8.3 Data Handling

In this study, no imputations for missing data will be completed. All analyses will be completed using observed data.

For pharmacokinetic analysis, the handling of concentration Data Below the Limit of Quantification (BLQ) will be completed as follows. For calculation of mean concentrations and generation of mean concentration-time profiles, all below the limit of quantification (BLQ) values will be set to zero except when an individual BLQ falls between two quantifiable values, in which case it will be treated as missing data.

For the pharmacokinetic analysis and individual concentration vs time plots, a concentration that is BLQ is assigned a value of zero if it occurs in a profile before the first measurable concentration. If a BLQ value occurs after a measurable concentration in a profile and is followed by a value above the lower limit of quantification, then the BLQ is treated as missing data. If a BLQ value occurs at the end of the collection interval (after the last quantifiable concentration) it is treated as missing data. In the case where less than 3 consecutive measurable concentrations of DFX is observed, the AUC parameters will not be estimated for that specific study period. If a predose concentration of DFX is detected, the patient's data can be included in the pharmacokinetic and statistical analysis without adjustment, if the predose concentration is equal to or less than 5% of the C_{max} value of the corresponding period. If the predose concentration is greater than 5% of the C_{max} value, the patient will be dropped from all pharmacokinetic and statistical evaluations.

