4 SELECTION AND WITHDRAWAL OF PATIENTS

The study will enroll up to 36 patients and no study drop-outs will be replaced. Patients who have provided written informed consent and an authorization for disclosure of protected health information must meet all of the following criteria to qualify for entry into the study.

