4.1 Inclusion Criteria

1. Written informed consent obtained prior to any study-related procedure being performed;
2. Patients at least 18 years of age or older at the time of consent;
3. Patient with TDT or NTDT syndromes and iron overload currently receiving iron chelation therapy with Jadenu or Exjade and demonstrating inadequate response assessed with serum ferritin and LIC;
4. Stable dosing with Jadenu or Exjade for >3 months prior to screening and receiving the maximal dose (Jadenu: 28 mg/kg or Exjade: 40 mg/kg);
5. Serum ferritin levels that are persistently >800 mcg/L determined by 2 separate assessments during screening over the previous 2-4 weeks prior to study treatment and not showing a decreasing trend over these weeks;
6. An LIC of >5 mg Fe/g dw measured by MRI in the 52 weeks prior to study entry;
7. Compliant with chelation therapy in the 3 months prior to enrollment as assessed by the Investigator:
 - a. Satisfaction with Iron Chelation Therapy (SICT) Quality of Life (QoL) composite score $\geq 60\%$, or determined by investigator that at least 75% of medication prescribed on a regular basis was taken (Investigator enquiry into patient prescription refill records, preferably 3 months if available); and
 - b. Willing to comply with chelation therapy for the duration of the study;
8. Agree not to use other anti-chelating agents concurrently;
9. Eastern Cooperative Oncology Group Performance Status (ECOG PS) of 0-1;
10. Women of childbearing potential (WOCBP) must use an adequate method of birth control (double barrier, e.g. hormonal control and barrier contraception) at least 28

days prior to the first administration of the study drug, during the study and for at least 30 days after the last dose of the study drug. (Section 7.5 for details);

11. Male patients whose partners are WOCBP must use an adequate method of birth control (double barrier control) at least 28 days prior to the first administration of the study drug, during the study and for at least 30 days after the last dose of the study drug; and
12. Patient is willing and able to comply with all protocol required visits and assessments.

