6.4.4 Visit 10 (Day 63 ±1 day)/Early Termination (ET)

Procedures as identified in Table 6.1.

- Washout Instructions
- Vital signs (blood pressure, heart rate, respiratory rate and body temperature)
- Physical Examination (full)
- Chemistry, Hematology (CBC) and Urinalysis
- Serum CRP
- Urine for protein and creatinine
- ECOG PS (see [Appendix C](#))
- Adverse Events
- Concomitant Medications
- Collect gastrointestinal AESI diary
- Collect Bristol Stool Chart diary
- Review gastrointestinal AESI diary
- Review Bristol Stool Chart diary
- Treatment Compliance
- Ferritin monitoring
- Pharmacokinetic sampling at predose (-0.5 hour) and 1, 2, 4, and 8 hours postdose (not performed for ET)

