6.6 Early Termination Procedures

The term "Early Termination" refers to a patient's non-completion of a study whether by his or her own choice or the Investigator's decision or due to discontinuation of the study by DisperSol.

In the absence of a medical contraindication or significant protocol violation, every effort will be made by the Investigator to keep the patient in the study. Should the patient decide to

withdraw, an attempt will be made to conduct an early termination visit, which will include all procedures normally done at Visit 10 (Day 63) and, the patient should be requested to undergo a 7-day washout and have a phone call to confirm as in the Follow-up (Day 70) procedures.

The primary reason for a patient withdrawing prematurely should be selected from the following categories:

Adverse Event or Serious Adverse Event - events that are associated with discontinuation.

Noncompliance with protocol - The patient failed to adhere to the protocol requirements. The deviation necessitated premature termination from the study.

Pregnancy - The patient became pregnant after enrolling the study. Pregnant patients are withdrawn from the study as soon as the Principal Investigator is aware of the condition.

Laboratory Abnormality - Laboratory abnormality that does not meet the definition of an AE.

Withdrawal of Consent - The patient desires to withdraw from further participation in the study in the absence of an adverse event or a medical need to withdraw.

Lost to Follow-up - The patient did not return for follow-up visit(s) following dispensing of test drug.

Other - causes of premature termination from the study other than the above, such as theft or loss of investigational product, termination of study by DisperSol, etc.

The Investigator should notify Accelovance, Inc. promptly when a patient is withdrawn, or if the study is stopped at his/her site by the IRB or if the Investigator elects to stop the study.

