7.10 Ferritin Monitoring

Ferritin (mcg/L) will be assessed in serum or plasma (at Screening, Eligibility and on Days 1, 28, 36 and 63) with enzyme-linked immunosorbent assays (ELISA) by routine laboratory methods.

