8.5 Statistical Analyses

A comprehensive statistical analysis plan (SAP) will be written and approved prior to database lock for this study that describes the final analyses to be completed for safety, efficacy, and pharmacokinetic endpoints.

Data collected in this study will be presented using summary tables, figures, and patient data listings. Summary tables will present data by treatment group and by time of collection. Continuous variables will be summarized using descriptive statistics, specifically the number of patients (n), the mean, median, standard deviation, minimum and maximum, and coefficient of variations (%CV). Categorical variables will be summarized by frequencies and percentages. Confidence intervals will be provided where appropriate for derived endpoints. Figures will be used to support the presentation of certain data. Sensitivity analyses may be performed to examine the effect of missing data.

All confidence intervals (CIs), statistical tests, and resulting p values will be reported as 2-sided. Significance will be assessed at $\alpha = 0.05$ level and the significance level will not be adjusted for multiple comparisons in the exploratory efficacy endpoint analyses.

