8.5.2 Efficacy Analyses

Planned efficacy analyses will include examination of changes in iron chelation. Analysis by TDT and NTD stratification will depend on recruitment status. Descriptive summaries of serum ferritin at each time point in each study period will be completed. Change from baseline in

serum ferritin will be assessed with a mixed model for repeated measures (MMRM) to assess changes within each treatment period and time. Categorical summaries will be presented for efficacy responders, i.e., the proportion of patients who achieve serum ferritin <800 mcg/L.

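### The observed-data-only rule in 8.3 gives no way to count a patient who stops a treatment without a ferritin as a non-responder, so the ferritin responder proportion is likely to be biased upward

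*Protocol*

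**What the plan says.** **Missing data.** Section 8.3 says: "In this study, no imputations for missing data will be completed. All analyses will be completed using observed data". Section 8.5 adds: "Sensitivity analyses may be performed to examine the effect of missing data". It does not say what those analyses would be.

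**Endpoint.** Section 8.5.2 says: "Categorical summaries will be presented for efficacy responders, i.e., the proportion of patients who achieve serum ferritin <800 mcg/L". This is a plain proportion with no model behind it.

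**Entry.** Section 4.1 requires "Serum ferritin levels that are persistently >800 mcg/L determined by 2 separate assessments during screening", with no downward trend.

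**Schedule.** Section 7.10 places ferritin "at Screening, Eligibility and on Days 1, 28, 36 and 63". Each treatment period therefore has one scheduled end-of-period value, Day 28 or Day 63.

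**Early termination.** Section 6.6 defines early termination as non-completion of the study for any reason. It asks sites to attempt a visit "which will include all procedures normally done at Visit 10 (Day 63". Section 6.4.4 lists ferritin among those procedures, and the only item it waives is "Pharmacokinetic sampling at predose (-0.5 hour) and 1, 2, 4, and 8 hours postdose (not performed for ET".

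**Populations and size.** The ITT population in 8.2 requires an evaluable efficacy value following the first DST-0509 dose. Section 4 says: "The study will enroll up to 36 patients and no study drop-outs will be replaced".

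**The concern.** The rule is fixed in the protocol for all analyses, so a later analysis plan that scored a missing ferritin as failure would depart from it. Section 4.3 lists toxicity, adverse events and noncompliance among the reasons for withdrawal, so missing values may depend on the treatment. A patient enters above 800 mcg/L and counts as a responder only by falling below it. One who stops without a later value most plausibly did not respond, and removing that patient raises the proportion relative to all who took the drug.

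Iron-chelating activity compared with Jadenu or Exjade is part of the primary objective (2.1). At most 36 patients are enrolled, so a few missing values visibly move a proportion.

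**Working it through.** **The plan's own figure.** The only design calculation concerns diarrhea events (8.1). At a 12% rate and N = 30, 1 - 0.88^30 = 0.978 for at least one event, and 0.890 for at least two. These match the stated 98% and 89%. They say nothing about response or drop-out, for which the protocol gives no rate.

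**Inputs.** From the protocol: up to 36 patients, 18 per sequence. Assumed for illustration: the number of responders x, the number m without a usable ferritin, and the stopping rates.

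**Formulas**, for N patients treated with a drug and d = m/N:
- observed-case rate = x/(N - m)
- all-treated rate, missing counted as non-response = x/N
- relative overstatement = N/(N - m) = 1/(1 - d)
- absolute overstatement = x/(N - m) - x/N = (observed-case rate) × d

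The factor 1/(1 - d) is an upper limit. It is reached if none of the missing patients would have responded, and it shrinks towards 1 as their response rate approaches that of the observed patients.

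**One drug, N = 36:**

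| Responders x | Missing m | Observed-case | All-treated |
|---|---|---|---|
| 4 | 2 | 11.8% | 11.1% |
| 4 | 4 | 12.5% | 11.1% |
| 4 | 7 | 13.8% | 11.1% |
| 7 | 4 | 21.9% | 19.4% |
| 7 | 7 | 24.1% | 19.4% |

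**Both drugs, 18 per sequence, assumed stopping of 20% on drug A and 5% on drug B.** A patient who stops in Period 1 never starts the second drug.
- A: treated 18 + 18 × 0.95 = 35.1; missing 35.1 × 0.20 = 7.0; factor 35.1/28.1 = 1.25.
- B: treated 18 + 18 × 0.80 = 32.4; missing 32.4 × 0.05 = 1.6; factor 32.4/30.8 = 1.05.
- If half of the stoppers have an early-termination ferritin that is counted: 1.11 and 1.03.
- If all have one that is counted: 1.00 for both.

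**Relative against absolute scale.** At an equal observed-case rate of 15%, with 20% and 5% missing, the absolute overstatement is 15 × 0.20 = 3.0 points and 15 × 0.05 = 0.75 points. At 5% response with 20% missing against 25% response with 5% missing, it is 5 × 0.20 = 1.0 point and 25 × 0.05 = 1.25 points, so the order reverses. Only the relative overstatement is always larger for the drug with more missing values.

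**The case against.** **The early-termination visit collects ferritin.** This largely stands. A reader might infer from the schedule table, where the early-termination visit shares a column with Visit 10 in Period 2, that a Period 1 stopper gets no ferritin. Section 6.6 does not support that: early termination covers non-completion at any time, and ferritin is retained. Two gaps remain. The visit is only attempted, and no section says whether its ferritin counts as the end-of-period value for the drug stopped.

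**Observed data do not fix a denominator, and a responder count over all treated patients imputes nothing.** This is fair as logic, so the loss of these patients follows from an observed-case reading and is not an explicit instruction. Denominators are also commonly left to the analysis plan. But the protocol does not offer the all-treated denominator. Its nearest population, ITT, already leaves out a patient with no efficacy value after DST-0509. It also leaves out a Sequence B patient who withdraws on the comparator, which is a separate selection not caused by 8.3.

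**Sections 8.3 and 8.5 might look contradictory.** They are in tension only. A missing-data sensitivity analysis need not impute; comparing ITT with Per Protocol is one example.

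**The stakes are low.** This stands. Section 8.1 calls chelating activity preliminary, and 8.5.2 attaches no test to the responder summary.

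**Conclusion.** The point holds as a minor one. Taken at its word, 8.3 provides no way to count a treated patient without a usable ferritin as a non-responder, and the likely result is an upward bias of at most 1/(1 - d). With d assumed at 5% to 20%, this is 1.05- to 1.25-fold, falling to none if every stopper has an early-termination value that is counted. The direction rests on the entry criterion: missing patients are taken to respond less often than observed ones.

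Two stronger readings are not supported. First, a reader might take N = 24, 30 and 36 in 8.1 as completer counts and derive an inflation of up to 36/24 = 1.5. Those are sample-size scenarios for observing a diarrhea event, and 1.2 says fewer patients may be enrolled depending on recruitment. Second, a reader might conclude that the less tolerated drug is always favored. That is assured only on the relative scale, and only if missingness follows tolerability.

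**What to change.** Add to 8.3, as an exception to the no-imputation rule:

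*For the ferritin responder endpoint, the denominator for each treatment is every patient who took one or more doses of that treatment, regardless of the efficacy-measurement requirement of the ITT population. A ferritin from an early-termination visit is used as the end-of-period value for the treatment being taken when the patient stopped. A patient with neither a Day 28/Day 63 ferritin nor an early-termination ferritin for that treatment is counted as a non-responder.*

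The reference to ITT is needed because 8.2 would otherwise still exclude some of these patients. The early-termination sentence is needed so that an observed value below 800 mcg/L is not overridden. Keep the observed-case proportion as a sensitivity summary, and leave the ferritin change model on observed data.

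The cost is a short paragraph, one extra table and somewhat lower responder rates. A patient who completes the period but misses the blood draw would also count as a non-responder; the observed-case summary shows how much that matters.

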8. Other criteria, at the Investigator's discretion in consultation with the Medical Monitor.

DOSAGE FORMS AND ROUTE OF ADMINISTRATION:

DST-0509 will be supplied in 360 mg, 180 mg and 90 mg tablets. Jadenu is commercially available as tablets and Exjade as tablets for oral suspension and will be provided by the patient with their ongoing prescription. Dosing will be at equivalent (mg for mg) doses of DST-0509 or Jadenu. If converting from Exjade, the dose will be scaled for each treatment by 28 mg/40 mg (treatment/Exjade).

This is an open-label crossover study. Patients will receive Exjade or Jadenu at their previous stable dose. DST-0509 is taken with food, Jadenu is taken with or without a light meal, and Exjade is recommended to be taken without food. However, either Jadenu or Exjade can be administered according to the patient's previous regimen.

OUTCOME VARIABLES:

The primary outcome of the study will be the safety, overall tolerability, and preliminary evidence of DST-0509 iron chelating activity compared to Jadenu or Exjade.

Iron chelation

Serum ferritin will be assessed at screening (Visits 1 and 2) and on Days 1, 28, 36 and 63. Change from baseline in each treatment period will be assessed as the main efficacy variable for serum ferritin.

Efficacy responders, i.e., the proportion of patients who achieve serum ferritin <800 mcg/L, will be evaluated.

Pharmacokinetics

Trough deferasirox levels will be collected in the Screening period at approximately -4 and -2 weeks. Blood samples for PK analysis will be collected predose (-0.5 hour for trough level) and at 1, 2, 4, and 8 hours post dose on Days 1, 7, 28, 36, 42 and 63. The PK parameters of DST-0509 and Jadenu or Exjade will be derived from the concentration time data. The allowed sampling "window" is ± 15 min for the 1 and 2 hour time points, and ± 30 min for the 4 hour time point. For the 8 hour time point, the allowable window is ± 1 hour.

The goal of the PK analyses will be to characterize the PK of the inadequate responder population on their current DFX therapy at the end of 4 weeks compared to 4 weeks of therapy with DST-0509. The hypothesis is that a significant proportion of inadequate responders will have low exposures on current therapy compared to exposure with DST-0509.

Exploratory Pharmacogenomics

A blood sample will be taken at Visit 2 to collect germline DNA to allow for later exploratory sub-analyses of genotype vs exposures.

SAFETY AND TOLERABILITY ASSESSMENTS:

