DST-0509 is manufactured using a thermokinetic mixing process, or fusion process to produce drug-polymer composites, and specifically an amorphous drug-polymer intermediate. The process has been repeatedly demonstrated in the pharmaceutical literature to produce amorphous drug-polymer intermediates with compounds that could not be successfully melt-extruded owing to their high melting points. The composition provides improved DFX solubility and dissolution properties that may result in enhanced bioavailability and reduced pharmacokinetic variability in patients. These attributes are expected to translate into less variability in response, and improved efficacy in non-responders as compared to existing marketed DFX products.

The FDA approved initial dose of Exjade is 20 mg/kg and may be titrated up to 40 mg/kg [1]. The dosing of Jadenu is initially 7 or 14 mg per kg body weight (depending on the indication) orally, once daily [2]. The maximum recommended dosage of Jadenu is 28 mg per kg body weight orally, once daily [2]. Galanello, et al reported that ICL670 (Exjade) was well tolerated, and no safety problems occurred up to 80 mg/kg following administration of a single dose [4].

DFX is absorbed following oral administration with median times to maximum plasma concentration (T_{max}) of about 1.5 to 4 hours. The C_{max} and AUC of DFX increase approximately linearly after both single administration and under steady-state conditions. Exposure to DFX increased by an accumulation factor of 1.3-2.3 after multiple doses. The absolute bioavailability (AUC) of DFX tablets for oral suspension is 70% compared to an intravenous dose. The bioavailability (AUC) of DFX was variably increased when taken with a meal [1,2].

DFX is highly (~99%) protein bound almost exclusively to serum albumin. The percentage of DFX confined to the blood cells was 5% in humans. The volume of distribution at steady-state of DFX is 14.37 ± 2.69 L in adults. Glucuronidation is the main metabolic pathway for DFX, with subsequent biliary excretion.

DFX and metabolites are primarily (84% of the dose) excreted in the feces. Renal excretion of DFX and metabolites is minimal (8% of the administered dose). The mean elimination half-life ($t_{1/2}$) ranged from 8-16 hours following oral administration [1,2]

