3.1 Overall Study Design

This is a multi-center, open-label, two-period cross-over, patient-pilot study comparing DST-0509 to Exjade or Jadenu administered orally once daily (QD) for 28-days in each period, with a 7-day washout before study entry and between treatment periods (see Table 6-1). Patients will be randomized to one of two treatment sequences: DST-0509→Exjade/Jadenu or Exjade/Jadenu→DST-0509 (with subjects who were taking Exjade prior to study start receiving Exjade and those taking Jadenu at study start receiving Jadenu). This study is designed to assess the safety, tolerability, evidence of iron chelating activity, and PK profile of DST-0509 compared to Jadenu or Exjade in inadequately responding patients. Inadequate response to standard chelation therapy is defined from the medical literature [6,7].

Up to 36 patients will be randomized 1:1 into one of two treatment sequences (study arms), of which up to 100% may be on Jadenu or Exjade at study entry, or a mix of the two. The planned randomization will assign up to 18 patients in each of two sequences: Sequence A: DST-0509 crossed to Exjade or Jadenu; Sequence B: Jadenu or Exjade crossed to DST-0509. The comparator treatment will be the patient's current chelation treatment. At the end of the study, patients previously on Jadenu or Exjade will revert to receiving their pre-study medication and dose following a 7-day washout period. A sufficient number of patients will be enrolled so there will be no need to replace study drop-outs. Study duration is approximately 14 weeks for each patient. A Study Flow Diagram is presented after this Synopsis (see Figure 3-1).

Figure 3-1: Study Flow Diagram

Treatment A (28 days) = DST-0509
Treatment B (28 days) = Jadenu/Exjade¹

*Up to 36 patients are planned.

- Subjects taking Exjade prior to study start will receive Exjade (treatment B) in the assigned Period 1 or cross-over Period 2. Those patients taking Jadenu prior to study start will receive Jadenu (treatment B) in the assigned Period 1 or cross-over Period 2. Dosing will be at equivalent (mg for mg) doses of DST-0509 for Jadenu. If crossing over from Exjade to DST-0509, or vice versa, the dose will be scaled to 28 mg/40 mg (DST-0509/Exjade).
- For all patients entering the trial, a 7-day washout is required.

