6.3.2 Visit 4 (Day 7 ±1 day)

Procedures as identified in Table 6-1.

- Adverse Events
- Concomitant Medications
- Review GI AESI diary
- Review Bristol Stool Chart diary
- Treatment Compliance
- Pharmacokinetic sampling at predose (-0.5 hour) and 1, 2, 4, and 8 hours postdose
- Patients are instructed not to take study medication on the morning before they arrive for their next visit

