7.11.2 Pharmacokinetics

Trough samples will be collected at Visit 1 and 2. Blood samples for PK analysis will be collected predose (-0.5 hour) and at 1, 2, 4, and 8 hours postdose on Days 1, 7, 28, 36, 42 and 63. The allowed sampling “window” is ± 15 min for the 1 and 2 hour time points, and ± 30 min for the 4 hour time point. For the 8 hour time point, the allowable window is ± 1 hour.

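### The 5% predose exclusion in Section 8.3 is not limited to the first-dose days, so read literally it drops most to nearly all adherent patients for having an ordinary steady-state trough

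*Protocol*

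**What the plan says.** Section 8.3 (Data Handling) lets a patient with a detectable predose concentration stay in the analysis without adjustment "if the predose concentration is equal to or less than 5% of the C_{max} value of the corresponding period". It then adds: "If the predose concentration is greater than 5% of the C_{max} value, the patient will be dropped from all pharmacokinetic and statistical evaluations". Neither sentence names a study day.

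Section 7.11.2 schedules PK blood samples "predose (-0.5 hour) and at 1, 2, 4, and 8 hours postdose on Days 1, 7, 28, 36, 42 and 63". Treatment is "administered orally once daily (QD) for 28-days in each period" (Section 3.1), with a 7-day washout before each period. Days 1 and 36 therefore follow a washout, and Days 7, 28, 42 and 63 lie within daily dosing. The visit instructions ensure that the sample on those four days is a true trough: "Patients are instructed not to take study medication on the morning before they arrive for their next visit" (Section 6.3.2).

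The synopsis gives the PK goal as to "characterize the PK of the inadequate responder population on their current DFX therapy at the end of 4 weeks" and to compare this with 4 weeks on DST-0509. Table 8-1 plans multiple-dose Cmin, Cavg, percent fluctuation, Clss/F and AUC over the dosing interval.

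**The concern.** A limit on the predose concentration makes sense as a carry-over check after a washout, where the expected value is close to zero. On a day within once-daily dosing, a substantial predose concentration is the intended observation. Section 8.3 makes that observation a ground for exclusion, and the exclusion covers the whole patient rather than one profile. One failing day is enough.

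At stake are the multiple-dose half of the secondary objective, the steady-state rows of Table 8-1 and the week-4 comparison. A patient could pass all four dosing days only by eliminating the drug unusually fast or by having missed doses before the visits, so those who remain would not represent the treated population.

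**Working it through.** The protocol quotes no figure that rests on the 5% rule, so there is nothing to reproduce first. The check asks what predose/Cmax ratio the protocol's own PK figures imply.

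**Inputs**
- Half-life (t½): the mean "ranged from 8-16 hours following oral administration" (Section 1.1).
- Tmax: median 1.5 to 4 h (Section 1.1).
- Dosing interval: 24 h. The predose sample is drawn 0.5 h before the dose, so 23.5 h after the previous one.
- Accumulation: "Exposure to DFX increased by an accumulation factor of 1.3-2.3 after multiple doses" (Section 1.1).
- Washout: 7 days, 168 h.
- Between-patient CV of half-life: not given. Assumed 20% to 50%, lognormal.

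**Step 1. Expected trough during daily dosing.** Two methods:
- (a) simple decline from the peak, 2^(−(23.5 − Tmax)/t½);
- (b) a one-compartment model with first-order absorption at steady state, with the absorption rate solved from Tmax (first-dose or steady-state peak time; the range covers both).

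| Mean t½ | (a) Tmax 1.5 h | (a) Tmax 4 h | (b) range |
|---|---|---|---|
| 8 h | 2^(−22/8) = 14.9% | 2^(−19.5/8) = 18.5% | 15–22% |
| 12 h | 2^(−22/12) = 28.1% | 2^(−19.5/12) = 32.4% | 29–36% |
| 16 h | 2^(−22/16) = 38.6% | 2^(−19.5/16) = 43.0% | 39–46% |

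The range is about 15% to 46%. Against the limit that is 15/5 = 3 to 46/5 ≈ 9 times.

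**Step 2. Half-life needed to pass.** Setting (a) to 5% gives t½ = ln 2 × (23.5 − Tmax)/ln 20: 5.1 h at Tmax 1.5 h and 4.5 h at Tmax 4 h. Both lie below the lowest quoted mean of 8 h.

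**Step 3. A sharper peak.** Take the case closest to the limit (t½ 8 h, Tmax 1.5 h, 15.4% in the model). Raise Cmax by the 30% formulation effect and the 29% high-fat-meal effect quoted in the Jadenu label (Appendix B, 12.3), leaving the trough alone: 15.4%/(1.30 × 1.29) = 9.2%. This is still above 5%.

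**Step 4. Cross-check from accumulation.** With R = 1/(1 − f), where f is the fraction left after 24 h, f = 1 − 1/R. R = 1.3 gives 23% and R = 2.3 gives 57%. A fraction of 5% would need R = 1/0.95 = 1.05. The half-life range itself implies R of 1.14 to 1.55, which overlaps the quoted range without matching it. Both sources put f well above 5%.

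**Step 5. Share of adherent patients dropped.** This is the share whose half-life exceeds the Step 2 break-even, over the assumed CVs and both Tmax values:

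| Mean t½ | Share dropped | Of 36 |
|---|---|---|
| 8 h | 76% to 99.7% | 27.5 to 35.9 |
| 12 h | 94% to 100% | 33.9 to 36 |
| 16 h | 99% to 100% | 35.5 to 36 |

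**Step 6. The same rule on Days 1 and 36.** In the one-compartment model, the concentration left 167.5 h after the last steady-state dose is 0.12% to 0.14% of first-dose Cmax at t½ 16 h, about 0.01% at 12 h and practically zero at 8 h. The ±1-day windows allow a Day 28 visit on Day 29 and a Day 36 visit on Day 35. That gap is 144 h, and carry-over at 16 h becomes about 0.3% to 0.4%. On these two days the 5% limit works as a carry-over check.

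**The case against.** The best counter-argument is that the intended scope is narrower than the text. The rule compares predose with Cmax "if the predose concentration is equal to or less than 5% of the C_{max} value of the corresponding period", which in a two-period crossover sounds like a between-period carry-over check. The protocol elsewhere calls the predose sample a trough and plans separate single-dose and multiple-dose parameters, so a sensible analyst would hardly apply the rule to Day 28. The PK Population is fixed after review of the concentrations, with reasons listed, and full PK detail is left to the SAP.

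The likely intent may well be as described, but the text does not state it. A period in this protocol is the 28-day treatment block, which holds Days 1, 7 and 28 (or 36, 42 and 63), so the phrase does not narrow the rule. The sentence on too few measurable concentrations, just before, confines its consequence to one study period, whereas this one reaches the whole patient. No section exempts the dosing days. This is an explicit rule rather than detail left to the SAP, and a SAP that narrowed it would depart from the protocol. Deciding exclusions after seeing concentrations in an open-label study is a reason for a rule that can be followed as written.

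Other parts of the objection do stand and limit the point:
- A reader might infer that no trough can fall to 5%, or that no analysable patients would remain. The 8 to 16 h are mean half-lives of marketed deferasirox. Individual spread and a half-life for DST-0509 are not given, so some patients could pass.
- A reader might infer that the survivors are selected for poor absorption, the subject of the PK hypothesis. Section 1.1 describes Cmax and AUC as roughly linear in dose. Low bioavailability then scales trough and peak alike and leaves the ratio unchanged. Selection acts on elimination rate and missed doses.
- A reader might take the words about statistical evaluations to empty the safety and ferritin analyses as well. The sentence sits in a paragraph on PK handling, and the Safety and ITT definitions in Section 8.2 do not refer to it.

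**Conclusion.** The rule is wrong as written. On the four dosing days it treats the expected trough, about 15% to 46% of Cmax, as a reason to drop the patient, and so contradicts the week-4 goal and the multiple-dose parameters in Table 8-1. The ratio rests on the protocol's own half-life and Tmax and on linear one-compartment behaviour. Two methods agree, and the accumulation factor points the same way. The loss of about 76% to 100% of adherent patients at a mean half-life of 8 h, and 94% to 100% at 12 to 16 h, also depends on the assumed CV. Most to nearly all is the supportable statement; all is not.

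PK is a secondary objective of a pilot study sized on adverse events. Sampling and dosing do not depend on the rule, so it can be corrected at any time before database lock without loss of data.

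**What to change.** In Section 8.3, and in the SAP to match:
1. Limit the 5% rule to the predose samples of Day 1 and Day 36, each compared with the Cmax of that day's first-dose profile, and make the consequence exclusion of that first-dose profile only.
2. State that predose concentrations on Days 7, 28, 42 and 63 are steady-state troughs, are not subject to exclusion under the 5% rule, and are analysed as troughs.

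The second sentence should not promise that such a value can never be set aside. An implausible result, for example one pointing to a dose taken before the visit, may still be excluded for a documented reason.

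The cost is two sentences. It needs no extra samples, visits or patients. It should be settled before the concentration data are reviewed for PK Population membership.
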